6.3.4 Toxicology

Dose range-finding studies (non-Good Laboratory Practice [GLP]) in mice (CD-1) and cynomolgus monkeys have been performed. In both species, 2-part studies have been performed, consisting of a dose range-finding portion with an escalating single dose administered by IV or SC injection, followed by a fixed, repeated dose portion with 3 dose level (DLs) administered for 14 days (dosed every other day). The studies included toxicokinetics, analyzing RGT100-PEI levels in plasma on the first and last days of treatment, and histopathology of selected organs and the injection sites.

In addition, non-GLP studies have been performed in mice to evaluate clinical effects (blood biomarkers: cytokines, hematology, and clinical chemistry) and desensitization after repeated dosing of RGT100-PEI.

Two 28-day IV repeated dose, GLP toxicity studies have also been performed in mice and cynomolgus monkeys. In both studies, the dosing frequency of RGT100-PEI was every other day. Both studies included a toxicokinetic part, analyzing RGT100-PEI plasma levels on the first and last days of treatment. Safety pharmacology assessments were also built into the studies. Overall, the studies demonstrated good tolerability up to the maximal feasible doses in both species, with no observed adverse effect levels (NOAELs) of 1.6 mg/kg and 0.16 mg/kg for mice and monkeys, respectively.

6.4 Dose Selection and Justification

Based on the pharmacodynamic data and the dose/tumor size correlation observed (refer to IB, Section 4.2.1.4), 0.2 mg RGT100 can be considered a pharmacologically active dose for intratumoral injection when extrapolated from tumors in mice to a human lesion with a diameter of 20 mm.

Accordingly, a starting dose (DL1) of 1 mL (0.2 mg) of RGT100-PEI is being considered for the first-in-human clinical study of intratumoral/intralesional injection into cutaneous or hepatic lesions. Results from the 4-week toxicity studies in mice and cynomolgus monkeys suggest the following NOAELs and human equivalent doses (HEDs) after IV administration of RGT100-PEI:

- NOAEL/maximum tolerated dose (MTD) in mice = 1.6 mg/kg IV → HED = 0.13 mg/kg
- NOAEL in cynomolgus monkeys = 0.16 mg/kg → HED = 0.05 mg/kg
- MTD in cynomolgus monkeys = 1.5 mg/kg → HED = 0.5 mg/kg

Leakage of RGT100-PEI from the lesion after intratumoral injection is expected to be marginal because, after intratumoral injection in mice, 100% of the compound remained local

(refer to IB, Section 4.2.1.4). However, for the calculation of safety margins, complete leakage (eg, accidental administration into a blood vessel) was used as a worst case assumption. A theoretical complete leakage from a cutaneous lesion was mimicked in the SC toxicity studies. Local toxicity after direct injection into the liver was not examined, but results from a preliminary biodistribution study showed that most RGT100 is found in the liver after IV injection. Therefore, the IV toxicity data can be used to extrapolate the safety of leakage into healthy liver tissue.

Thus, assuming a theoretical complete systemic ad hoc exposure after intratumoral administration, a starting dose of 1 mL (0.2 mg RGT100) in a 60 kg human (0.0033 mg/kg) would lead to the following safety factors (calculated with unrounded raw data):

- Safety factor for mouse NOAEL/MTD: $0.13/0.0033 = 40$
- Safety factor for cynomolgus monkey NOAEL: $0.05/0.0033 = 15$
- Safety factor for cynomolgus monkey MTD: $0.5/0.0033 = 150$

Of note, the safety factor of 40 for the mouse has been calculated based on the NOAEL/MTD of 1.6 mg/kg (HED = 0.13 mg/kg) observed in the pivotal 4 week toxicity study. Nevertheless, in single-dose IV studies in mice (LPT studies 32867 and 33090) at a dose of 2 mg/kg (HED = 0.16 mg/kg) or 3 mg/kg RGT100-PEI, acute clinical signs and mortality were observed within 2 hours after administration of RGT100-PEI. Therefore, the safety factor for the minimum lethal dose is 48. Because this safety factor is based on the worst case assumption of complete leakage, it is considered acceptable for the intended patient population with advanced cancer.

6.5 Clinical Experience with RGT100-PEI

There are no prior or ongoing clinical trials in humans investigating RGT100-PEI. The first-in-human trial will evaluate the safety, tolerability, and anti-tumor activity of intratumoral/intralesional injections of RGT100-PEI in subjects with selected advanced or recurrent tumors.

6.6 Potential Risks and Benefits

Given that RGT100-PEI has not yet been tested in humans and this is a first-in-human study, the potential side effects of injecting this drug into humans are unknown. To date, RGT100-PEI has shown an acceptable safety profile for intratumoral/intralesional injection in animals. There has been a lack of any major side effects or toxicities in animal treated with RGT100-PEI.

Potential risks associated with the administration of RGT100-PEI based on nonclinical data may include the following:

- Immune-related adverse events (irAEs) (including colitis, hepatitis, thyroid complications) based on the fact that the mode of action of RGT100 revolves around the immune system
- Hypersensitivity reactions at the injected tumor site (skin rashes, pruritus or urticarial, flu-like symptoms such as fever, chills, muscle aches, fatigue, and headache, diarrhea, nausea and vomiting and low blood pressure)

- Altered liver function (increases in alanine transaminase [ALT], aspartate transaminase [AST], and lactate dehydrogenase [LDH], decreases in erythrocyte counts, hemoglobin levels, and hematocrit)
- Local reactions at the injected tumor site (swelling, induration, and erythema)

6.7 Rationale for the Study

Nonclinical studies have demonstrated that RGT100-PEI, a cytosolic receptor molecule for intratumoral/intralesional injection, induces a potent innate as well as adaptive immune response based on RIG-I activation in nonclinical studies.

This Phase 1/2 multicenter, first-in-human, open-label, dose escalation study will evaluate the safety, tolerability, and anti-tumor activity of intratumoral/intralesional injections of RGT100-PEI in subjects with selected advanced or recurrent tumors.

Results from this Phase I/II study will support further clinical development of RGT100-PEI. This study will be performed in compliance with the protocol, International Council for Harmonisation (ICH) Good Clinical Practice (GCP),⁵ and local regulatory requirements. Aspects of the study concerned with manufacture and labelling of RGT100-PEI will meet the requirements of Good Manufacturing Practice.

7 STUDY OBJECTIVES AND ENDPOINTS

7.1 Objectives

The primary objectives of the study are to:

- Evaluate the safety and tolerability of intratumoral/intralesional injections of RGT100-PEI
- Determine the recommended Phase 2 dose (RP2D) feasible for intratumoral/intralesional injections of RGT100-PEI

The secondary objective of the study is to:

- Explore preliminary anti-tumor activity of RGT100-PEI on injected and un-injected tumor lesions

The exploratory objectives of the study are to:

- Investigate the type of cytokine release in plasma upon treatment
- Investigate the pharmacokinetics (PK) of RGT100-PEI in subjects with advanced or recurrent tumors
- Explore potential predictive biomarkers of tumor responses upon intratumoral/intralesional RGT100-PEI therapy*
- Evaluate the impact of RGT100-PEI therapy on immune infiltration of injected tumors*

*These exploratory objectives will be evaluated in a separate sub-study. Results of these exploratory investigations will not be presented as part of the main Clinical Study Report.

7.2 Endpoints

The primary endpoints of the study are:

- Incidence and severity of treatment-related adverse events (AEs) and laboratory abnormalities, graded according to National Cancer Institute Common Terminology Criteria for Adverse Events (NCI CTCAE) version 4.03 criteria
- Occurrence of serious adverse events (SAEs)
- Occurrence of treatment discontinuation due to treatment-related AEs
- Incidence and severity of dose-limiting toxicities (DLTs)

The secondary endpoint of the study is:

- Objective response rate as evaluated radiologically using immune-related Response Evaluation Criteria in Solid Tumors (irRECIST)

The exploratory endpoints of the study are:

- Type of cytokine release in plasma
- Plasma concentrations of RGT100-PEI and, where feasible, standard PK parameters
- Presence of predictive biomarkers of tumor responses*
- Evidence of immune infiltration of injected tumors*

*These exploratory objectives will be evaluated in a separate sub-study. Results of these exploratory investigations will not be presented as part of the main Clinical Study Report.

8 INVESTIGATIONAL PLAN

8.1 Overall Study Design and Plan: Description

[figure not shown]
This is a Phase I/II multicenter, first-in-human open-label, dose escalation study to evaluate the safety, tolerability, and anti-tumor activity of intratumoral/intralesional injections of RGT100-PEI in subjects with selected advanced or recurrent tumors.

The study will be conducted in 2 groups (Group A and Group B) with each group consisting of a dose escalation phase followed by an expansion phase.

Each phase of the study will consist of a screening period, treatment period, end of treatment visit and a follow-up period.

A schematic diagram of the study design is presented in [Figure 1](#).

Figure 1: Study Design

8.1.1 Dose Escalation Phase

This phase of the study will investigate increasing DLs of RGT100-PEI to determine the MTD or maximum feasible dose (MFD). The MFD is the highest dose volume that is safe and tolerable, and is feasible for intralesional/intratumoral injection. The MFD may be lower

than the MTD. The MTD (or MFD if lower than MTD) will define the RP2D to be used in the expansion phase of the study.

RGT100-PEI will be at a fixed concentration of 0.2 mg/mL and dose escalation will be based on the total volume of RGT100-PEI injected per subject. The planned DLs to be investigated in this phase of the study are:

- DL1: 0.2 mg = 1 mL
- DL2: 0.4 mg = 2 mL
- DL3: 0.6 mg = 3 mL
- DL4: 0.8 mg = 4 mL*

*Dose escalation may continue if deemed appropriate by the Safety Review Committee (SRC) (refer to [Section 10.5](#) for SRC details). The corresponding next dose levels beyond the above and the supporting safety data to continue will be described within a substantial amendment to this protocol which will only be implemented once approval has been received.

It is not expected that a MTD will be reached at the proposed dose levels. It is more likely that a maximum feasible dose will be reached before the MTD, defined as the maximum volume which can be injected into a lesion. Experience with other compounds which are also injected intratumorally/intralesionally was taken into consideration when planning the proposed dose levels and the initially proposed highest dose. However according to the nature of a phase I trial the maximum tolerable and/or feasible dose level are yet unknown and cannot be predicted.

The specific properties of RGT100-PEI being an immune-modulating drug is taken into consideration and safety will be closely monitored to detect any early signs of toxicity in general and dose limiting toxicities in particular.

For each DL the second and subsequent subject treated will start treatment at least 7 days following the first subject's injection to allow initial assessment of safety data by the treating Investigator and to report any serious potential safety concerns such as DLTs.

Group A will commence dosing first. Group B will commence dosing once DL2 has been shown to be safe and well tolerated in Group A subjects. Dosing will then commence at DL2 for Group B.

A standard 3 + 3 design ([Table 1](#)) will be used for dose escalation (3 subjects per DL group, with the potential to add an additional 3 subjects to a DL group if toxicity is observed).

Table 1: Standard 3+3 Dose Escalation Scheme

Number of Subjects with a DLT at a Given Dose Level (during the DLT period)	Action
0 out of 3 subjects experience a DLT	Escalate to the next DL
1 out of 3 subjects experiences a DLT	Enter 3 additional evaluable subjects at the current DL for a total of 6 evaluable subjects
1 out of 6 subjects experiences a DLT	Escalate to the next DL

2 or more subjects (up to 6 subjects) experience a DLT	Dose escalation will be stopped (at this DL the MTD has been exceeded or declared)
--	--

Abbreviations: DL = dose level; DLT = dose-limiting toxicity; MTD = maximum tolerated dose.

If more than 2 subjects experience a DLT at a particular DL, a lower (or intermediate) DL may be explored to better define the MTD. Refer to [Section 8.4.6](#) for DLT definition and [Section 8.4.7](#) for MTD definition.

Approximately 9 to 24 subjects will be treated in each group during the dose escalation. All types of tumors that are accessible for intratumoral/intralesional injection may be treated in the dose escalation part of the study.

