8.4.6 Selection of Doses in the Study

The concentration of the RGT100-PEI particles in the injection dispersion is fixed to 0.2 mg/mL to achieve stable complexes. Volumes of RGT100-PEI will be escalated to provide total doses of, for example, 0.2, 0.4, 0.6, and 0.8 mg per injection.

The planned starting dose of 1 mL (0.2 mg) for the dose escalation phase of the study is based on pre-clinical data (refer to [Section 6.4](#) for dose justification). To date there are no human data for RGT100-PEI.

Subsequent dose escalation will be based on the safety findings of the previous dose following review by the SRC (refer to [Section 8.1.1](#) for dose escalation details).

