8.4.7 Dose-limiting Toxicity

The DLTs and MTD are defined using the NCI CTCAE version 4.03.

Dose-limiting toxicities will be drug-related toxicities (considered related or possibly related to) and graded using NCI CTCAE version 4.03 occurring during the DLT period and include:

- Non-hematologic toxicity \geq grade 3 (except diarrhea, nausea, and vomiting unless lasting >3 days despite optimal supportive care)
- Confirmed (with a second measurement after 24 hours) non-hematologic appropriately graded laboratory findings of grade ≥ 3 that were \leq grade 1 at baseline
- Hematologic toxicity:

- Grade 4 neutropenia ≥ 5 days, or grade 3 neutropenia with fever (fever is $> 38.4^{\circ}\text{C}$)
- Grade 4 thrombocytopenia, or grade 3 thrombocytopenia lasting > 7 days or with bleeding
- Any other toxicity assessed as related to RGT100-PEI, and which, in the opinion of the study Investigator(s) and the Sponsor physician constitutes a DLT

The DLT period will be 4 weeks. Evaluation of the available safety data over this DLT period will be required from at least 3 subjects per DL and per Group (A or B) before a decision is made whether to enroll additional subjects at the same, or the next DL.

Note: Subjects withdrawn from the study before the completion of the DLT period for reasons other than DLT will be replaced.

During dose escalation, escalation to the next DL will occur only if the safety and tolerability (including DLTs) data are acceptable as determined during the dose escalation meetings by the SRC. If any change is made to the grade or causality of an AE during the study that may alter its DLT status, the Sponsor and SRC must be informed immediately as this may affect dose escalation decisions.

The following toxicities will not be considered as DLTs:

- Grade 3 AE of tumor flare (defined as local pain, irritation, or rash localized at sites of known or suspected tumor)
- Grade 3 irAE that resolves to grade ≤ 1 within 7 days.

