8.4.8 Maximum Tolerated Dose, Maximum Feasible Dose, and RP2D

The MTD is defined as 1 DL below the DL where ≥ 2 of 6 subjects in a group experience a DLT for RGT100-PEI during the DLT period of 4 weeks. Maximum tolerated dose will be determined following discussion of all the relevant toxicity data by the SRC during the dose escalation meetings after each dose escalation step (refer to [Section 10.5](#) for SRC details).

If ≤ 1 of 6 subjects in all dose levels experience a DLT, then an MTD will not have been reached in this group. In this case, the RP2D will be selected based on integrated evaluation of safety, tolerability, clinical benefit, and pharmacodynamic data, for all DLs tested.

Once the MTD has been defined, dosing at a higher dose must not occur in this group. Once the MTD has been exceeded, the cohort at the next lowest DL will be expanded to 6 subjects if necessary and only 3 subjects were involved before. The SRC are free to decide on an intermediate DL.

The MFD is the highest dose volume that is safe and tolerable, and is feasible for intralesional/intratumoral injection in the respective group. The MFD may be lower than the MTD. The MTD (or MFD if lower than MTD) will define the RP2D to be used in the expansion phase of the study.

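### At exactly two DLTs, Table 1 and the sentence under it can be read as making that dose level the MTD, while Section 8.4.8 puts the MTD one level lower

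*Combined protocol and SAP*

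**What the plan says.** **Section 8.1.1, Table 1, last row.** The row applies when two or more subjects, out of up to six, have a DLT. The action is: "Dose escalation will be stopped (at this DL the MTD has been exceeded or declared". The row does not say when the MTD counts as exceeded and when as declared.

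**Section 8.1.1, sentence under Table 1.** "If more than 2 subjects experience a DLT at a particular DL, a lower (or intermediate) DL may be explored". The trigger here is one DLT higher than in the table row.

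**Section 8.4.8.** "The MTD is defined as 1 DL below the DL where ≥ 2 of 6 subjects in a group experience a DLT". It continues: "Once the MTD has been exceeded, the cohort at the next lowest DL will be expanded to 6 subjects if necessary", where only three were treated there before. It adds: "The SRC are free to decide on an intermediate DL".

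**Pointers under Table 1.** The reader is sent to 8.4.6 for the DLT definition and to 8.4.7 for the MTD definition. In the current numbering these are "8.4.6 Selection of Doses in the Study" and "8.4.7 Dose-limiting Toxicity". Neither pointer reaches 8.4.8.

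**The concern.** Read on its own, Section 8.1.1 yields a coherent rule. Exactly two DLTs: stop, and this level is the declared MTD. More than two: the MTD is exceeded, and a lower level may be explored. Section 8.4.8 gives a different rule, in which two DLTs are enough to put the MTD one level down. The thresholds differ (more than two against at least two), the force differs (optional against required), and the resulting MTD can differ by one level.

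Two wording gaps keep this open. Section 8.4.8 speaks of at least two of six, while Table 1 can stop at two of three. And the pointers in 8.1.1 do not lead to 8.4.8.

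Determining the RP2D is a primary objective (Section 7.1). Section 8.4.8 says that the MTD, or the maximum feasible dose if lower, defines it, and Section 11.1.6 makes the DLTs the basis for choosing it. There is also an effect before expansion. Section 8.4.8 bars dosing above the MTD in the group once it is defined. Second cycles repeat the subject's previous dose (8.4.9.3), and dose reductions are not allowed (8.4.9.4). Whether subjects from the stopping level could be re-treated may therefore depend on which reading is used.

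**Working it through.** **Inputs.** Dose levels of 0.2, 0.4, 0.6 and 0.8 mg (8.1.1); the stop/go rule (Table 1); the MTD definition (8.4.8). The documents give no DLT rate, so a true risk p of 5%, 10%, 20% or 30% at the stopping level is assumed. Subjects are taken as independent, and each cohort of three is fully evaluated before a decision.

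**The plan's own figure.** Section 11.2.1 gives 9 to 24 subjects per group. Three levels × 3 = 9 (Group B, DL2 to DL4) and four levels × 6 = 24, so the range follows from the 3+3 rule. The point does not depend on it.

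**The two sections side by side.**

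| DLTs at the level | Section 8.1.1 | Section 8.4.8 |
|---|---|---|
| 2 of 3 | Stop; MTD exceeded or declared here; step-down sentence not triggered | One level lower in substance, but not literally covered |
| 2 of 6 | Same | One level lower; that level filled to six |
| 3 of 3 | Stop; lower or intermediate level may be explored | One level lower in substance |
| 3 or 4 of 6 | Stop; lower or intermediate level may be explored | One level lower; that level filled to six |

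**Dose at stake.** Two of six at DL3: 0.6 or 0.4 mg, ratio 0.6/0.4 = 1.50. Two of six at DL4: 0.8 or 0.6 mg, ratio 0.8/0.6 = 1.33.

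**How often a stop falls on exactly two DLTs.** With q = 1 − p:

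- P(2 of 3) = 3p²q
- P(2 of 6) = (3pq²)², one DLT in each cohort of three
- P(escalate) = q³ + 3pq⁵, and P(stop) = 1 − P(escalate)
- P(stop within the first three) = 3p²q + p³

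| p | 5% | 10% | 20% | 30% |
|---|---|---|---|---|
| P(2 of 3) | 0.0071 | 0.0270 | 0.0960 | 0.1890 |
| P(2 of 6) | 0.0183 | 0.0590 | 0.1475 | 0.1945 |
| P(exactly two) | 0.0255 | 0.0860 | 0.2435 | 0.3835 |
| P(stop) | 0.0266 | 0.0939 | 0.2914 | 0.5057 |
| Exactly two, share of stops | 96% | 92% | 84% | 76% |
| More than two, share of stops | 4% | 8% | 16% | 24% |
| Within first three, share of stops | 27% | 30% | 36% | 43% |

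The shares depend only on the risk at the stopping level, so they apply to both groups.

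**Observed rate at the contested level.** 2/6 = 33% (exact 95% CI 4% to 78%) or 2/3 = 67% (9% to 99%). Table 1 allows escalation with at most 1/6 = 17% once six are treated.

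**Illustration over four levels.** Each reading is followed to the letter, with no later change after the lower level is filled. Reading 8.1.1: exactly two DLTs name that level, more than two name the one below. Reading 8.4.8: any stop names the one below. The table gives the chance that DL3 or DL4 is named the MTD.

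| Assumed risk, DL1 to DL4 | 8.4.8 | 8.1.1 reading |
|---|---|---|
| 5, 10, 20, 35% | 37.7% | 32.0 + 27.2 = 59.2% |
| 10, 20, 30, 45% | 24.3% | 33.0 + 15.9 = 48.9% |
| 5, 25, 40, 50% | 15.0% | 33.4 + 9.3 = 42.7% |

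Under 8.4.8, DL4 cannot be named, because no higher level is planned. One term in full (second row, DL4, 8.1.1 reading): DL4 is reached with probability 0.9061 × 0.7086 × 0.4943 = 0.3174. Exactly two DLTs at p = 0.45 has probability 0.3341 + 0.1668 = 0.5009. The product is 0.159.

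**The case against.** The strongest reply is that there is only one MTD definition. Table 1 is a stop/go scheme, and the text under it sends the reader elsewhere for the MTD. The wrong section number looks like a renumbering slip: Section 8.4.1 likewise cites 8.4.8.4 for what is now 8.4.9.4. The word *declared* can simply mean that the MTD determination is triggered. The sentence about more than two DLTs is permissive and forbids nothing at two. Two DLTs in three subjects already guarantee at least two of six. The 76% to 96% shares hold for any 3+3 design, rest on assumed rates, and do not give the chance that the SRC would choose the higher dose.

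The safeguards are also real. The SRC determines the MTD from all relevant toxicity data, its charter may say more, and Section 8.1.2 requires an amendment and authority acceptance of the RP2D before expansion. Section 8.1.1 does not expect an MTD at the planned levels, and if none is reached the conflict does not arise.

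Most of this stands. Section 8.4.8 should govern, the Table 1 reading is permitted and not forced, and a wrong RP2D is unlikely. It does not remove the mismatch. Section 8.1.1 offers two outcomes for the MTD, then a step-down trigger one DLT above the stopping threshold, and no correct pointer to the section that would settle it.

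**Conclusion.** The concern holds as an inconsistent threshold in a decision rule. At exactly two DLTs the text can support two MTDs one level apart: 0.6 or 0.4 mg at DL3 (50% higher) and 0.8 or 0.6 mg at DL4 (33% higher). Under assumed DLT risks of 5% to 30% at the stopping level, this is how 96% to 76% of stops would occur. The chance that a given level ends at exactly two DLTs is 3%, 9%, 24% or 38% at risks of 5%, 10%, 20% or 30%. These figures rest on the assumed rates, independent subjects and fully evaluated cohorts. They show how often the ambiguity would be met, not how often a wrong dose would be chosen.

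The practical harm is limited, because every reading stops escalation and both the SRC and the authorities stand between the rule and the expansion dose. It should still be corrected: the rule serves a primary objective of a first-in-human trial, and the looser reading would carry forward a level with 33% or 67% observed DLTs.

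**What to change.** Make Section 8.4.8 govern, by wording alone:

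1. Table 1, last row: delete the words that allow the MTD to be declared at the stopping level.
2. Sentence under Table 1: change the trigger from more than two DLTs to two or more. State that the next lower level is filled to six under 8.4.8 where only three were treated, and keep the SRC's option of an intermediate level.
3. Section 8.4.8: define the stopping level as one with at least two DLTs among up to six subjects, so that two of three is covered.
4. Pointers under Table 1: cite 8.4.7 for DLTs and 8.4.8 for the MTD.

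The cost is text in two sections at the next protocol amendment. No subjects are needed beyond those 8.4.8 already requires.

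These edits leave one related matter to the SRC. Group B starts at DL2, so a stop there would place the MTD at DL1, which is untested in that group. The SRC would have to decide whether to open DL1 before naming it.
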